5.2.2 Dose Modification

Every effort should be made to administer study treatments per the planned dosing schedule. Dose modification guidelines for a particular study treatment are to be followed if AEs are assessed as associated or potentially associated with that study treatment.

5.2.2.1 Dose Modification and Toxicity Management Guidelines for Adverse Events Potentially Associated with Pembrolizumab Treatment

Dose modification and toxicity management for immune-related AEs (irAEs) associated with pembrolizumab

Adverse events associated with pembrolizumab exposure may represent an immunologic etiology. These irAEs may occur shortly after the first dose or several months after the last dose of pembrolizumab treatment and may affect more than one body system simultaneously. Therefore, early recognition and initiation of treatment is critical to reduce complications. Based on existing clinical trial data, most irAEs were reversible and could be managed with interruptions of pembrolizumab, administration of corticosteroids, and/or other supportive care. For suspected irAEs, ensure adequate evaluation to confirm etiology or exclude other causes. Additional procedures or tests such as bronchoscopy, endoscopy, or skin biopsy may be included as part of the evaluation. Based on the severity of irAEs, withhold or permanently discontinue pembrolizumab and administer corticosteroids. Dose modification and toxicity management guidelines for irAEs associated with pembrolizumab are provided in [Table 6](#).

Table 6 Dose Modification and Toxicity Management Guidelines for irAEs Associated with Pembrolizumab

General instructions:				

 1. Corticosteroid taper should be initiated upon AE improving to Grade 1 or less and continue to taper over at least 4 weeks. 2. For situations where pembrolizumab has been withheld, pembrolizumab can be resumed after AE has been reduced to Grade 1 or 0 and corticosteroid has been tapered. Pembrolizumab should be permanently discontinued if AE does not resolve within 12 weeks of last dose or corticosteroids cannot be reduced to ≤ 10 mg prednisone or equivalent per day within 12 weeks. 3. For severe and life-threatening irAEs, IV corticosteroid should be initiated first followed by oral steroid. Other immunosuppressive treatment should be initiated if irAEs cannot be controlled by corticosteroids. 				

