LABORATORY PROCEDURES/ASSESSMENTS – Local Laboratory																	
Pregnancy Test ^t	X																
PT/INR ^u	X			X	X	X	X	X	X	X	X	X	X	X	X	X	
Hematology ^u	X			X	X	X	X	X	X	X	X	X	X	X	X	X	
Chemistry ^u	X			X	X	X	X	X	X	X	X	X	X	X	X	X	
Urinalysis ^u	X			X	X	X	X	X	X	X	X	X	X	X	X	X	
Thyroid Function Testing ^u	X			X	X	X	X	X	X	X	X	X	X	X	X	X	
LABORATORY PROCEDURES/ASSESSMENTS – Central Laboratory																	
PK ^{v,w}		X			X		X			X						X	
ADA ^v		X			X		X			X						X	
TUMOR BIOPSY/ ARCHIVAL TISSUE COLLECTION/BLOOD FOR CORRELATIVE STUDIES																	
Tumor Tissue Collection	X ^x																
Blood for genetic analyses ^y		X															
Blood for ctDNA analyses ^z		X		X			X								X		
Blood for TCR repertoire ^z		X		X			X								X		
Blood for RNA analyses ^z		X		X			X								X		

Trial Period:	Screening	Treatment Cycles (1 cycle = 21 days) ^a												End of Treatment	Post-Treatment		
		Cycles 1-8								To be repeated Beyond Cycle 12					Safety Follow-up 30 days from last dose ± 3	Imaging Follow-up Q6W or Q12W ^b (± 7)	Survival Follow-up Q12W ^c (± 7)
Scheduled Clinic Visit:	Screening	C1	C2	C3	C4	C5	C6	C7	C8	C9	C10	C11	C12	End of Treatment			
Clinic Visit Windows (Days):	-28 to -1	D1 ^a	D8	D1	D1	D1	D1	D1	D1	D1	D1	D1	D1				
Blood for plasma biomarker analyses ^z		X		X										X			
Blood for serum biomarker		X		X										X			

- a. Each treatment cycle in the pembrolizumab plus axitinib arm is 21 days ± 3 days. C1D1 denotes the first dose of study treatment, which can be on the date of randomization or within 3 days of randomization.
- b. Imaging follow-up visits are for subjects who have discontinued study treatment without reaching BICR verified or further investigator confirmed PD. See footnotes “n” and “o” for further details.
- c. Survival follow-up may be conducted as a telephone call or a clinic visit Q12W (visit window is ± 7 days through Week 104 and ± 14 days after Week 104). Survival contact may be requested more frequently at the time of interim and final analysis or an eDMC safety review (see Section 7.1.5.3.4).
- d. Written consent must be obtained prior to performing any protocol-specified procedures.
- e. The Subject Identification Card should be dispensed at Screening and collected at the End of Treatment visit.

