7.1.1.3 Subject Identification Card

All subjects will be given a Subject Identification Card identifying them as participants in a research trial. The card will contain trial site contact information (including direct telephone numbers) to be utilized in the event of an emergency. The investigator or qualified designee will provide the subject with a Subject Identification Card immediately after the subject provides written informed consent. At the time of treatment allocation/randomization, site personnel will add the treatment/randomization number to the Subject Identification Card.

The subject identification card also contains contact information for the emergency unblinding call center so that a health care provider can obtain information about trial medication/vaccination in emergency situations where the investigator is not available.

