7.1.5.3 Post-Treatment

7.1.5.3.1 End of Treatment

The End of Treatment Visit should occur at the time study treatment is discontinued for any reason. If the End of Treatment Visit occurs 30 days from the last dose of study treatment, at the time of the mandatory Safety Follow up Visit, the End of Treatment visit procedures and any additional Safety Follow-up procedures should be performed. Visit requirements are outlined in Section 6.0- Trial Flow Chart. Additional details regarding subject withdrawal and discontinuation are presented in Section 5.8– Subject Withdrawal/Discontinuation Criteria.

Subjects who discontinue trial treatment for reasons other than disease progression will **still be considered on study** and should continue with regularly scheduled assessments listed in the Imaging Follow-up Visit on the Trial Flow Chart (Section 6.0; also refer to Section 7.1.5.3.3).

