7.2.3 Immediate Reporting of Adverse Events to the Sponsor

7.2.3.1 Serious Adverse Events

A serious adverse event is any adverse event occurring at any dose or during any use of Sponsor's product that:

- Results in death;
- Is life threatening;
- Results in persistent or significant disability/incapacity;
- Results in or prolongs an existing inpatient hospitalization;
- Is a congenital anomaly/birth defect;
- Is an other important medical event.

Note: In addition to the above criteria, adverse events meeting either of the below criteria, although not serious per ICH definition, are reportable to the Sponsor in the same timeframe as SAEs to meet certain local requirements. Therefore, these events are considered serious by the Sponsor for collection purposes.

- Is a new cancer (that is not a condition of the study);
- Is associated with an overdose.

Refer to [Table 15](#) for additional details regarding each of the above criteria.

For the time period beginning when the consent form is signed until treatment allocation/randomization, any serious adverse event, or follow up to a serious adverse event, including death due to any cause other than progression of the cancer under study (reference Section 7.2.3.3 for additional details), that occurs to any subject must be reported within 24 hours to the Sponsor if it causes the subject to be excluded from the trial, or is the result of a protocol-specified intervention, including but not limited to washout or discontinuation of usual therapy, diet, placebo treatment or a procedure.

For the time period beginning at treatment allocation/randomization through 90 days following cessation of treatment or 30 days following cessation of treatment if the subject initiates new anticancer therapy, whichever is earlier, any serious adverse event, or follow up to a serious adverse event, including death due to any cause other than progression of the cancer under study (reference Section 7.2.3.3 for additional details), whether or not related to the Sponsor's product, must be reported within 24 hours to the Sponsor either by electronic media or paper. Electronic reporting procedures can be found in the EDC data entry guidelines. Paper reporting procedures can be found in the Investigator Trial File Binder (or equivalent).

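### The flow charts collect the emergency Subject Identification Card at End of Treatment, before the protocol's own post-treatment safety window closes

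*Combined protocol and SAP*

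**What the plan says.** Footnote e is worded identically in flow charts 6.1 (combination arm) and 6.2 (sunitinib): "The Subject Identification Card should be dispensed at Screening and collected at the End of Treatment visit". The card row in each chart agrees with it, with one mark at Screening and one at End of Treatment.

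Section 7.1.1.3 gives the card's purpose: "The card will contain trial site contact information (including direct telephone numbers) to be utilized in the event of an emergency". It adds that the card carries a call-centre contact, through which a health care provider can learn about the trial medication when the investigator cannot be reached. The card is handed over "immediately after the subject provides written informed consent". The section does not mention return, retention or re-issue.

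Section 7.1.5.3.1 sets the timing of collection: "The End of Treatment Visit should occur at the time study treatment is discontinued for any reason". It also allows for the visit to coincide with the 30-day Safety Follow-up Visit.

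Two other sections describe the period after treatment:

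- Section 5.2.2.1, on pembrolizumab: "These irAEs may occur shortly after the first dose or several months after the last dose of pembrolizumab treatment". It goes on to stress early recognition.
- Section 7.2.3.1, on SAE reporting from randomization: "through 90 days following cessation of treatment or 30 days following cessation of treatment if the subject initiates new anticancer therapy, whichever is earlier". SAEs considered related to the product remain reportable outside that period as well.

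The second-course chart (6.3) allows up to 17 further pembrolizumab cycles and has no card row.

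**The concern.** The card exists for a subject who falls ill away from the trial site, perhaps unable to give a history, and is seen by a physician who does not know about the trial. In the combination arm, a late immune-related event is a clear example, and the protocol itself says such events can come after dosing has ended. Collecting the card when treatment stops removes the aid while the protocol still regards the subject as at risk and still wants SAEs reported.

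Two things could suffer. The treating physician may be slower to link the event to a checkpoint inhibitor, and the site may hear of an outside SAE late or not at all. The first is a matter of subject safety. The second bears on how complete the post-treatment SAE data are. The documents give no reason for taking the card back.

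**Working it through.** No sample size, event count, power or alpha enters here, and the plan gives no figure to reproduce. The check sets the time points side by side and uses day arithmetic.

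**Inputs**

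- Card collected: at the End of Treatment visit (footnote e, 6.1 and 6.2).
- Earliest usual timing of that visit: when treatment is discontinued, taken here as day 0 (7.1.5.3.1).
- Latest timing described: combined with the Safety Follow-up Visit at day 30 ± 3, so day 27 to day 33 (7.1.5.3.1, 7.1.5.3.2).
- SAE window closes: day 90, or day 30 if new anticancer therapy starts (7.2.3.1).
- Second course: up to 17 cycles (6.3) of 21 days.

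**SAE days without a card** = day the SAE window closes − day the card is collected

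| Situation | Calculation | Gap |
|---|---|---|
| No new therapy, visit at day 0 | 90 − 0 | 90 days |
| No new therapy, visit combined, early edge | 90 − 27 | 63 days |
| No new therapy, visit combined, late edge | 90 − 33 | 57 days |
| New therapy, visit at day 0 | 30 − 0 | 30 days |
| New therapy, visit at about day 30 | 30 − 30 | about 0 days |

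**Late immune-related events.** The two clocks start at different points. The risk in 5.2.2.1 is counted from the last pembrolizumab dose, whereas the card is collected when study treatment ends. Under Section 2.1, a subject still progression-free after 35 pembrolizumab doses, or one who stops pembrolizumab alone for toxicity, continues axitinib. Such a subject keeps the card for some or all of the late-risk period. A subject who stops both drugs together loses it at the start of that period. In the sunitinib arm this argument falls away and only the SAE window remains.

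**Second course.** Section 2.1 allows study treatment to stop after a confirmed CR. If both drugs stop, End of Treatment follows and the card is collected. On progression, Section 5.8.3 may then permit up to 17 × 21 = 357 days of further treatment. Neither chart 6.3 nor Section 7.1.1.3 says that a card is re-issued, and neither says that it is withheld.

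**The case against.** The strongest reply is that the card is not the only safeguard.

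- **Knowledge of treatment.** The trial is open-label and subjects know what they received (5.2.4). They hold a copy of the signed consent form (7.1.1.1.1), and Section 10.3 notes the recommendation to inform the primary physician if the subject agrees. The call-centre route on the card is described as an unblinding service, which adds little where nothing is blinded.
- **Continued contact.** There is a mandatory safety visit at about day 30. Imaging visits every 6 or 12 weeks follow for subjects without verified progression, and survival contacts about every 12 weeks for the others. The AE row in the charts continues into follow-up.
- **No contradiction in the strict sense.** Nothing in the protocol says the card must span the SAE window.

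Much of this stands. It limits the harm that can be claimed, and no document shows that SAEs are being lost. It does not explain why the card is taken back. A subject in survival follow-up may have no scheduled clinic visit between day 30 and day 90, and a subject too ill to speak gains little from knowing the treatment.

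A reader might also infer stronger points that the documents do not support:

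- **That every subject lacks the card for the full 90 days.** The window shortens with new therapy, and the visit may fall near day 30.
- **That the 120-day pregnancy window is compromised.** It has the same 30-day cut-off with new therapy, and Section 7.2.2 concerns pregnancies spontaneously reported to the investigator, which do not depend on an emergency card.
- **That second-course subjects carry no card.** This rests only on the missing row in 6.3. After 35 doses a subject may still be on axitinib, so End of Treatment need not have occurred. Whether such a subject can enter the second course is itself unclear from Sections 2.1, 5.8.3 and 7.1.4.1.

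**Conclusion.** The mismatch is real and comes from an express instruction in both charts. The card is collected before the protocol's own post-treatment safety window closes. Without new anticancer therapy, the gap is up to 90 of 90 SAE days, or about 57 to 63 days if the visits are combined. With new therapy it is about 0 to 30 days. These figures assume that sites follow footnote e as written and that End of Treatment falls between the last dose and about day 30.

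The late immune-related risk adds weight in the combination arm only, chiefly for subjects who stop both drugs at or near the same time. For the second course, the most that can be said is that no re-issue is stated for a subject whose card was collected after stopping both drugs for CR.

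The documents give no rate of late events, so the number affected cannot be estimated. No endpoint, alpha level or analysis changes. The point merits action because the correction is nearly free and the documents offer no reason against it.

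**What to change.** - In footnote e of 6.1 and 6.2, delete the clause that has the card collected at End of Treatment. Let subjects keep the card at least until SAE reporting closes under 7.2.3.1.
- Move the End of Treatment mark in the card row of both charts to match.
- State in 7.1.1.3 how long the card is kept. State there and in 6.3 that it is retained or re-issued for a second course.

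The cost is a minor protocol text change, with whatever ethics review that requires, and an occasional replacement card for a subject who has already handed one in. No visit or procedure is added.

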6.2 Trial Flow Chart (Sunitinib)

Trial Period:	Screening	Treatment Cycles (1 cycle = 42 days) ^a											End of Treatment	Post-Treatment			
		Cycles 1-4										To be repeated Beyond Cycle 6					
Treatment Cycle:	Screening	C1			C2			C3		C4		C5	C6	Discon	Safety Follow-up	Imaging Follow-up	Survival Follow-up
Scheduled clinic visit:		D1 ^a	D15	D29	D1	D29	D1	D29	D1	D29	D1	D1					
Clinic visit Windows (Days):	-28 to -1		± 3	± 3	± 3	± 3	± 3	± 3	± 3	± 3	± 3	± 3	End of Treatment	30 days from last dose (± 3 days)	Q6W or Q12W ^b (± 7 days)	Q12W ^c (± 7 days)	
ADMINISTRATIVE PROCEDURES																	
Informed Consent ^d	X																
Informed Consent - FBR (optional)	X																
Inclusion/Exclusion Criteria	X																
Subject Identification Card ^e	X												X				
Demographics & Medical History	X																
Prior and Concomitant Treatment/Medication Review ^f	X	X	X	X	X	X	X	X	X	X	X	X	X	X			
Post-study Anti-cancer Therapy Status														X	X	X	
Survival Status ^g		←-----														X	
STUDY DRUG ADMINISTRATION/ COMPLIANCE																	
Sunitinib Dosing ^h		X [scheduled dosing is 4 weeks on (D1-D28) and 2 weeks off (D29-D42) for each cycle] from C1D1															
Dispense Sunitinib and Dosing Diary ⁱ		X			X		X		X		X	X					
Review Sunitinib Compliance ⁱ					X		X		X		X	X	X				

Trial Period:	Screening	Treatment Cycles (1 cycle = 42 days) ^a											End of Treatment	Post-Treatment				
Treatment Cycle:	Screening	Cycles 1-4										To be repeated Beyond Cycle 6		Discon	Safety Follow-up	Imaging Follow-up	Survival Follow-up	
		C1			C2			C3		C4		C5	C6					
Scheduled clinic visit:		D1 ^a	D15	D29	D1	D29	D1	D29	D1	D29	D1	D1			End of Treatment	30 days from last dose (± 3 days)	Q6W or Q12W ^b (± 7 days)	Q12W ^c (± 7 days)
Clinic visit Windows (Days):	-28 to -1		± 3	± 3	± 3	± 3	± 3	± 3	± 3	± 3	± 3	± 3	± 3					
CLINICAL PROCEDURES/ ASSESSMENTS																		
AE Monitoring	X	X	X	X	X	X	X	X	X	X	X	X	X	X	X	X ⁱ	X ⁱ	
Full Physical Examination	X													X				
Directed Physical Examination			X	X	X	X	X	X	X	X	X	X	X					
Vital Signs ^k	X		X	X	X	X	X	X	X	X	X	X	X	X	X	X		
12-Lead ECG ^l	X						X					X			X			
KPS ^m	X			X	X	X	X	X	X			X	X		X			
EFFICACY MEASUREMENTS – TUMOR IMAGING																		
Chest, Abdomen, Pelvis	X ⁿ																X ^p	
Bone Scan	X ^{n,q}																X ^q	
Brain Scan	X ^{n,r}																X ^r	
PATIENT REPORTED OUTCOMES																		
QoL (FKSI-DRS, EORTC QLQ-C30, EQ-5D-3L) ^s		X		X	X	X	X	X	X	X	X	X	X	X	X	X		
LABORATORY PROCEDURES/ ASSESSMENTS – Local Lab																		
Pregnancy Test ^t	X																	
PT/INRu ^t	X			X	X	X	X	X	X			X	X	X	X			
Hematology ^u	X			X	X	X	X	X	X			X	X	X	X			
Chemistry ^u	X			X	X	X	X	X	X			X	X	X	X			
Urinalysis ^u	X			X	X	X	X	X	X			X	X	X	X			
Thyroid Function Testing ^u	X			X	X	X	X	X	X			X	X	X	X			

Trial Period:	Screening	Treatment Cycles (1 cycle = 42 days) ^a											End of Treatment	Post-Treatment						
Treatment Cycle:	Screening	Cycles 1-4										To be repeated Beyond Cycle 6		Discon	Safety Follow-up	Imaging Follow-up	Survival Follow-up			
		C1			C2			C3		C4		C5	C6							
Scheduled clinic visit:		D1 ^a	D15	D29	D1	D29	D1	D29	D1	D29	D1	D1								
Clinic visit Windows (Days):	-28 to -1		± 3	± 3	± 3	± 3	± 3	± 3	± 3	± 3	± 3	± 3	± 3	± 3	± 3	± 3	End of Treatment	30 days from last dose (± 3 days)	Q6W or Q12W ^b (± 7 days)	Q12W ^c (± 7 days)
TUMOR BIOPSY/ ARCHIVAL TISSUE COLLECTION/ BLOOD FOR CORRELATIVE STUDIES																				
Tumor Tissue Collection	X ^v																			
Blood for genetic analyses ^w		X																		
Blood for ctDNA analyses ^x		X		X			X								X					
Blood for TCR repertoire ^x		X		X			X								X					
Blood for RNA analyses ^x		X		X			X								X					
Blood for plasma biomarker analyses ^x		X		X											X					
Blood for serum biomarker analyses ^x		X		X											X					

a. Each treatment cycle in the sunitinib arm is 6 weeks long (42 days ± 3 days). C1D1 denotes the first dose of study treatment, which can be on the date of randomization or within 3 days of randomization. See Section 5.2.3.4 for scenarios regarding dose interruptions.

b. Imaging Follow-up visits are for subjects who have discontinued study treatment without reaching BICR verified or further investigator confirmed PD. See footnotes “n” and “o” for further details.

c. Survival Follow-up may be conducted as a telephone call or a clinic visit Q12W (visit window is ± 7 days through Week 104 and ± 14 days after Week 104). Survival contact may be requested more frequently at the time of interim and final analysis or an eDMC safety review (see Section 7.1.5.3.4).

d. Written consent must be obtained prior to performing any protocol-specified procedures.

e. The Subject Identification Card should be dispensed at Screening and collected at the End of Treatment visit.

f. Prior treatments/medications: record **all** prior treatment for RCC. Record all medications taken within 30 days prior to the first dose of trial treatment. Concomitant medications: enter new medications started during the trial and up to 30 days after last dose of trial treatment regardless of when the safety follow-up visit occurs. All medications related to reportable SAEs and ECIs should be recorded as defined in Section 7.2.

g. Following verification of disease progression by BICR or further confirmation by the investigator, or the start of new anticancer treatment; contacts are approximately every 12 weeks by telephone. Updated survival status may be requested by the Sponsor at any time during the course of the study. Upon Sponsor notification, all participants who do not/will not have a scheduled study visit or study contact during the Sponsor defined time period will be contacted for their survival status (excluding participants that have a death event previously recorded).

h. Trial treatment should begin within 3 days of randomization for sunitinib. See Section 5.2.3 for dose administration details.

Trial Period:	Screening	Treatment Cycles (1 cycle = 42 days) ^a											End of Treatment	Post-Treatment				
Treatment Cycle:	Screening	Cycles 1-4										To be repeated Beyond Cycle 6		Discon	Safety Follow-up	Imaging Follow-up	Survival Follow-up	
		C1			C2			C3		C4		C5	C6					
Scheduled clinic visit:		D1 ^a	D15	D29	D1	D29	D1	D29	D1	D29	D1	D1			End of Treatment	30 days from last dose (± 3 days)	Q6W or Q12W ^b (± 7 days)	Q12W ^c (± 7 days)
Clinic visit Windows (Days):	-28 to -1		± 3	± 3	± 3	± 3	± 3	± 3	± 3	± 3	± 3	± 3	± 3					

i. Subjects will be given a dosing diary for sunitinib when sunitinib bottles are provided; the diary should be returned at the next visit and assessed for dosing compliance. See details in Section 7.1.1.9.
 
j. After the end of treatment, each subject will be followed for 30 days for AE monitoring (SAEs will be collected for 90 days after the end of treatment or 30 days after the end of treatment if the subject initiates new anti-cancer therapy, whichever is earlier). See Section 7.2.3.1 for details.
 
k. Vital Signs will be assessed at Screening (within 10 days of randomization), Day 15 and Day 29 of C1 and Day 1 and Day 29 C2 to C4, then Day 1 of all subsequent visits, the End of Treatment visit and the Safety Follow-up visit. C1D15 will only collect BP and pulse rate. Height will only be collected at Screening and will be recorded in the vital signs form. See Section 7.1.2.4 for BP assessments at baseline and during treatment.
 
l. An ECG is performed at Screening (within 10 days of randomization), after the completion of every 2 cycles (12 weeks) on treatment (C3D1, C5D1, C7D1, C9D1,...) and Safety Follow-up.
 
m. KPS is assessed at Screening (within 10 days of randomization), on Day 29 of C1, Day 1 and D29 of cycle C2-C3, Day 1 of every cycle thereafter (C4D1, C5D1, C6D1,...) and Safety Follow-up.
 
n. Baseline imaging must be performed within 28 days prior to randomization. Scans performed as part of routine clinical management are acceptable for use as the screening scan if they are of diagnostic quality and performed within the 28 day window. See Section 7.1.2.7.1 for additional imaging requirements at baseline and follow-up in subjects with RCC metastatic lesions identified outside of the standard imaging assessment anatomic regions per protocol.
 
o. Imaging after randomization will be performed at Week 12 (84 days ± 7 days), then Q6W (42 days ± 7 days) through Week 54, then Q12W (84 days ± 7 days) thereafter until PD is BICR verified or further confirmed by the investigator. Imaging visit window can be ± 14 days after Week 104. Unscheduled imaging can be performed as clinically indicated. The timing of imaging assessments should follow calendar days from randomization and should not be adjusted for dose delays or cycle starts. Imaging anatomic coverage should be the same as that at screening; see Section 7.1.2.7.2 for details.
 
p. Subjects who discontinue treatment for reasons other than BICR verified PD should continue with imaging assessments per the protocol defined schedule as outlined in footnote n until: 1) PD is BICR verified or further confirmed by investigator, 2) initiation of a new anti-cancer treatment, 3) death, 4) withdrawal of consent or 5) study conclusion or early termination, whichever occurs first. See footnote B for Imaging Follow-up schedule and windows.
 
q. Baseline bone scan is required for all subjects. If a subject has a positive baseline bone scan, after randomization, bone scans will be performed at Week 18 (126 days ± 7 days) and should continue to be performed Q12W (84 days ± 7 days) through Week 54. After Week 54, subsequently Q24W (168 days ± 7 days) through Week 54 until PD is BICR verified or further confirmed by investigator. The timing of imaging assessments should follow calendar days from randomization and should not be adjusted for dose delays or cycle starts. Bone scans must be performed for the confirmation of Complete Response (CR) for subjects with a positive bone scan at baseline.
 
r. A brain scan will be performed during screening for subjects with brain metastasis to ensure subject is stable. During the trial, brain imaging should be performed as clinically indicated and to confirm a CR in subjects with brain metastasis at baseline.
																		

Trial Period:	Screening	Treatment Cycles (1 cycle = 42 days) ^a											End of Treatment	Post-Treatment				
		Cycles 1-4										To be repeated Beyond Cycle 6						
Treatment Cycle:	Screening	C1			C2			C3			C4		C5	C6	Discon	Safety Follow-up	Imaging Follow-up	Survival Follow-up
Scheduled clinic visit:		D1 ^a	D15	D29	D1	D29	D1	D29	D1	D29	D1	D1				30 days from last dose (± 3 days)	Q6W or Q12W ^b (± 7 days)	Q12W ^c (± 7 days)
Clinic visit Windows (Days):	-28 to -1		± 3	± 3	± 3	± 3	± 3	± 3	± 3	± 3	± 3	± 3			End of Treatment			

s. At each clinic visit, Quality of Life (QoL) measurements should be performed before all other study procedures and assessments, including the dosing of study medication. QoL will be assessed D1 and D29 visits of C1-C4; D1 visit of C5 to C10, and D1 visit of every other cycle from C10 (D1C10, D1C12) (approximately Week 54) until study treatment is discontinued. In addition, QoL is to be assessed at the Treatment Discontinuation visit and 30-day Safety Follow-up visit. QoL is only assessed once if these two visits are combined.
 
t. Pregnancy tests – Urine or Serum β-hCG: See Section 5.1.2 for pregnancy tests requirements for screening. If the randomization pregnancy test is more than 72 hours prior to the first dose of trial treatment, it should be repeated. If urine pregnancy results are positive or cannot be confirmed as negative, a serum pregnancy test performed by the local study site laboratory will be required. Pregnancy tests (serum and/or urine tests) should be repeated if required by local guidelines. Monthly pregnancy testing should be conducted as per local regulations where applicable.
 
u. PT/INR, hematology, chemistry, urinalysis and thyroid function testing will be performed at Screening (within 10 days of randomization), C1D29, C2D1, C2D29, C3D1, C3D29, Day 1 of every cycle thereafter (C4D1, C5D1, C6D1,...), the End of Treatment visit and the Safety Follow-up visit.
 
v. Tumor tissue from an archival tissue sample or newly obtained biopsy should be submitted at screening for biomarker analysis.
 
w. Samples should be collected for planned analysis of the association between genetic variants in germline/tumor DNA and drug response. If a documented law or regulation prohibits (or if the IRB/IEC does not approve) sample collection for these purposes, then such samples should not be collected at the corresponding sites. Leftover DNA extracted from planned genetic samples will be stored for Future Biomedical Research only if the subject signs the FBR consent. If the planned genetic analysis is not approved, but FBR is approved and consent is given, this sample will be collected for the purpose of FBR.
 
x. Blood for ctDNA, TCR repertoire, RNA analyses and blood for serum/plasma biomarker analyses should be collected pre-dose according to time points on the flow chart. Leftover samples may be kept for Future Biomedical Research if the subject signs the FBR consent.
																		

